### Treatment Assignment Procedures

Randomization will be generated using PROC PLAN in SAS 9.3 by a biostatistician who is part of the University of Cincinnati's Center for Clinical and Translational Science and Training (CCTST). The CCTST biostatistician will not have access to the data. This data management support service will generate randomization and will assign a Treatment A/Treatment B designation. The randomization schedule and code sheet will be held confidentially by a senior Clinical Research Manager in the study mentor's ([name]) lab, and the study

interventionist ([name]) will contact the Clinical Research Manager to get the next assignment when a participant is enrolled in the study.

Gender and age will be used as blocking variables in randomization. Specifically, there will be four randomization tables for gender (male and female) by age (younger i.e., 11-13 years of age and older i.e., 14-16 years of age) combination:

- $11 \leq \text{Age} < 14$ , Female
- $14 \leq \text{Age} < 17$ , Female
- $11 \leq \text{Age} < 14$ , Male
- $14 \leq \text{Age} < 17$ , Male

Patients will be randomized to either ADAPT or WL. A separate randomization list will be produced for each of the four (4) blocks – Age x Sex. Per study protocol, a list of 10 treatment / control assignments will be produced per group. Within each group, a completely randomized design will be applied to allocate ADAPT or WL.

The test randomization and final randomization will require four seed numbers, one for each block size. The seed numbers below are for illustration only and will not be used.

- $11 \leq \text{Age} < 14$ , Female: Seed = 111111
- $14 \leq \text{Age} < 17$ , Female: Seed = 222222
- $11 \leq \text{Age} < 14$ , Male: Seed = 333333
- $14 \leq \text{Age} < 17$ , Male: Seed = 444444

The independent statistician will select seed numbers and will not share those final seed numbers with the project statistician ([name]) nor other members of the project team. The randomization identification number (rand\_id) will be comprised of 4 digits. The first digit will correspond to the blocks and the remaining 3 digits will be in sequential order, as listed below.

- Block 1:  $11 \leq \text{Age} < 14$ , Female. ID numbers 1001-1010
- Block 2:  $14 \leq \text{Age} < 17$ , Female. ID numbers 2011-2020
- Block 3:  $11 \leq \text{Age} < 14$ , Male. ID numbers 3021-3030
- Block 4:  $14 \leq \text{Age} < 17$ , Male. ID numbers 4031-4040

Given that other factors such as pubertal status and subjective pain levels could influence the outcome, these factors will be included in the analysis as control covariates. Each participant's exact age will be recorded at assessment allowing personnel to control for age as an additional covariate should the need become apparent during preliminary analyses.

## **Blinding**

- **Procedure for retaining the blind.** Blinding of study personnel will be employed when possible (Table 1). Of note, our study statistician ([name]) will only have access to subject IDs and Treatment A and Treatment B. He will generate monitoring reports for closed sessions based only on Treatment A and Treatment B. If there is an issue of serious concern

(e.g., safety issues in one arm, differential attrition etc.) that requires complete unblinding, [name] will identify another statistician to run the unblinded reports. [name] will also complete final analysis only by Treatment A versus B and the code will be revealed only after the data has been analyzed. Furthermore, the PI ([name]) will be blinded to group assignment. However, [name] will not be blinded to group assignment as study interventionist and to ensure the safety of participants and the integrity of the study. It is critical for [name] (a licensed clinical psychologist) to be aware of participants who are randomized to the ADAPT intervention in order to ensure patient safety (e.g., risk assessment for suicidal ideation, trauma/abuse, etc.) during the study. The PI ([name]) and study mentors ([name], [name]) will have no access to post-assessment data by group assignment until after the completion of the study.

- **Individual authorized to break the blind.** [name] will be authorized to break the blind. She will not be blinded to group assignment and therefore can determine if the study team's blind should be broken in cases where a patient's safety is in question. [name] extensive experience as a pediatric psychologist make her appropriately equipped to manage this responsibility.
- **Circumstances for breaking the blind.** The blind will be broken at the clinical discretion of [name]. Circumstances for breaking the blind may include cases when a patient's safety is at risk, differential attrition, or if a patient's symptoms remarkably worsen throughout treatment.
- **Procedure for breaking the blind.** If the blind needed to be broken, [name] would communicate with our local IRB, any NCCIH members involved in the study, and involve our study team, included but not limited to the PI ([name]), co-mentors ([name], [name]), the study statistician ([name]), and the outcome assessors.

### 9.3 Definition of Populations

Our intent-to-treat population (modified ITT) will be defined as those subjects who complete a post-randomization assessment.

### 9.4 Interim Analyses and Stopping Rules

There are no planned interim analyses. [name] will assess adherence and retention. If the treatment is deemed to be ineffective, unsafe, futile, or if there is evidence of poor study performance (e.g., slow accrual, high losses-to-follow-up, and poor quality control), a safety review may be warranted. This action would occur in consultation with the study mentors ([name], [name]), the IMC, and NCCIH. Examples of findings that might trigger a safety review are the number of SAEs overall, the number of occurrences of a particular type of SAE, severe AEs/reactions, or increased frequency of events. Such findings are presented to the study statistician ([name]) or to the IMC statistician to review the events by group to determine whether there are statistical as well as clinical concerns. The statistician reports his

findings to a closed session of the IMC or to the Safety Officer and/or NCCIH. The findings are used to determine what steps will be taken.

## **9.5 Outcomes**

### **9.5.1 Primary Outcome**

Subjects will first complete localizer sequences for targeting of other series. A B0 field map (B = magnetic field) will be used to correct for distortion due to susceptibility artifacts. A high resolution T1 weighted anatomical volume will be obtained to provide a detailed view of brain anatomy. Functional connectivity will be examined using the Blood Oxygenation Level Dependent (BOLD) effect.

### **9.5.2 Secondary Outcomes**

Brain activation during the WL-SPT will be assessed by arterial spin labeling (ASL). In order to examine relationships between resting brain activity and other variables, cerebral blood flow (CBF) will be measured in a quantitative fashion via ASL, which is the optimal for assessing steady-state conditions. Nine series will be obtained (5-10 mins each): Pre-WL-SPT: 1 MPRAGE; 2 resting ASLs; 2 resting BOLDs; post-WL-SPT: 2 ASLs; and 2 BOLDs.

## **9.6 Data Analyses**

For fMRI analysis, image processing and data analysis will be accomplished by FSL software. Each subject's functional images will be registered to their structural data using a six-parameter linear 3D transformation and then nonlinearly warped to standard space (MNI152). Analyses of both BOLD and ASL data will be accomplished via mixed effects ANOVAs. Data will be coded prior to analysis to conceal patient status to ensure blinding.

Clusters of activation will be identified using a threshold of  $Z > 3.1$  and statistical significance will be estimated according to Gaussian random field theory. Functional connectivity analysis will be conducted (Aim 1) to identify changes in functional connectivity between the AMY-PFC in ADAPT completers vs. those in the waitlist condition. A seed to whole brain analytic approach will be used to identify any/all differences observed. Pain-related brain activations are expected to diminish for those that complete ADAPT compared to the waitlist condition (Aim 2). For the exploratory aim, mechanisms associated with a positive treatment response (decreased pain intensity/ unpleasantness/ anxiety during WL-SPT) after ADAPT will be identified. Normalization of abnormal connectivity patterns are predicted to categorize changes in pain and anxiety. Specifically, decreases in brain activations and reductions in functional connectivity will be examined in relation to improvements in pain and anxiety post treatment using multiple (linear) regression.

While all efforts will be made to minimize missing data through the use of electronic data capture and real-time adherence data collection, missing data is still inevitable in RCTs. Thus, we will employ several strategies to handle missing data with specific attention on how to handle missing not-at-random. Specifically,

missing data will be handled via ML estimation with auxiliary correlate inclusion (e.g., Graham, 2003; Enders, 2010). Missing not at random will be addressed with mixture MNAR methods (e.g., Gottfredson, Bauer, & Baldwin, 2014; Muthen, et al., 2011; Sterba & Gottfredson, 2015).

Given that other factors such as pubertal status and subjective pain levels could influence the outcome, these factors will be included in the analysis as control covariates. Each participant's exact age will be recorded at assessment allowing personnel to control for age as an additional covariate should the need become apparent during preliminary analyses.

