## **5.4 Adherence Assessment**

The projected sample size is not adequately powered to account for differences in adherence. However, data will be collected on the attendance of Zoom-based sessions, completion of web-based content, and completion of therapist videoconferencing/phone calls, in addition to completing study assessments. We anticipate good adherence (>80% completion of intervention materials) based on our prior research. If adherence becomes problematic during the course of the study, the interventionist ([name]) will communicate these concerns with the PI ([name]).

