## 8. INTERVENTION DISCONTINUATION

- **Criteria for discontinuing intervention:** A participant will be considered discontinued if they explicitly state that they would like to withdraw from the research study and cease participation in the intervention or if study staff is unable to contact the child or their guardian after 2 weeks.
- **Possible reasons for discontinuation:** Based on prior research, common reasons for discontinuing the ADAPT intervention include scheduling difficulties and the participants' lack of proximity to the medical center. It will be continually reinforced throughout the intervention that participation is optional. Families will be informed if new treatments become available. The intervention will be discontinued if a participant experiences an increase in distress and pain symptoms throughout the intervention, or if the interventionist ([name]) determines that a participant's presentation warrants more targeted care outside of what the intervention offers. Given [name] expertise in pediatric pain psychology, she is well-suited to provide clinical oversight to make this determination. The intervention will be discontinued for all participants in the event of a study closure by the institute.
- Participation will be discontinued at any time at participant or parent request. Participants will continue to be followed with their permission if study intervention is discontinued. Should a randomized participant prematurely discontinue participation in the study, study measures and endpoints will continue to be collected if possible. Of note, based on prior research, if a participant discontinues the behavioral intervention it is unlikely that they will be retained for subsequent assessment visits. However, every effort will be made to collect endpoint and study measure data.

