## 9. STATISTICAL CONSIDERATIONS

### 9.1 General Design Issues

The statistical hypotheses:

**Aim 1.** Left AMY-PFC functional connectivity will be significantly diminished (i.e., evidence of decreased hyperconnectivity) during the water load symptom provocation task (WL-SPT) post ADAPT vs. waitlist.

**Aim 2.** Brain activations associated with cognitive (PFC), affective (pgACC, AMY), and visceral afferent (INS, thalamus, aMCC, S1 & S2) pain will significantly be more diminished after ADAPT vs. waitlist.

*Exploratory Aim.* Changes in functional connectivity and brain activations following ADAPT will correspond to reductions in pain (intensity and unpleasantness) and anxiety ratings.

The choice of study design (blinded clinical trial) will enable us to answer these research questions.

Primary and secondary outcome measures are obtained from neuroimaging data. The brain regions selected have been shown in prior literature to be related to chronic pain and response to psychological interventions for the management of chronic pain conditions.

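### Section 9.6 words the primary comparison as ADAPT completers versus waitlist, section 9.3 defines a different set, 'completer' is undefined, and no section says which set is primary

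*Combined protocol and SAP*

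**What the plan says.** Section 9.6 states that the Aim 1 analysis is to "identify changes in functional connectivity between the AMY-PFC in ADAPT completers vs. those in the waitlist condition". Its Aim 2 sentence is a prediction with similar wording: "Pain-related brain activations are expected to diminish for those that complete ADAPT compared to the waitlist condition".

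Section 9.3 has one definition: "Our intent-to-treat population (modified ITT) will be defined as those subjects who complete a post-randomization assessment". It mentions no aim, and 9.6 does not mention the modified intent-to-treat set.

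The Aim 1 hypothesis in section 9.1 concerns connectivity "during the water load symptom provocation task (WL-SPT) post ADAPT vs. waitlist", with no condition on completing treatment. Sections 1.1 and 3 are the same in this respect.

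Section 8 has three relevant parts:
- On who counts as discontinued: "A participant will be considered discontinued if they explicitly state that they would like to withdraw from the research study" and stop the intervention, or if the family cannot be reached for two weeks.
- On why children stop: "common reasons for discontinuing the ADAPT intervention include scheduling difficulties", along with distance from the centre. It also ends the intervention when distress and pain increase, or when the interventionist judges that more targeted care is needed.
- On follow-up: endpoint data are still sought after discontinuation (section 10.1 agrees), with the warning that "if a participant discontinues the behavioral intervention it is unlikely that they will be retained for subsequent assessment visits".

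Section 5.4 adds: "The projected sample size is not adequately powered to account for differences in adherence". It anticipates better than 80% completion of the materials. That is a forecast of adherence, not a definition of a completer.

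**The concern.** A completion condition of this kind can act on one arm only, because waitlist children have no ADAPT sessions to finish before their post scan. Selecting on behaviour after randomization in one arm and not in the other gives up the protection of randomization for the primary contrast.

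Stopping may also be related to outcome. Scheduling and distance look unrelated to brain response, but section 8 has a symptom-based route out of the intervention, and the exploratory aim predicts that connectivity change tracks pain and anxiety. A child who stops because symptoms worsen could therefore differ on the primary outcome as well.

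Finally, with no definition of a completer and no named primary set, two analysts could follow the plan in good faith, choose different sets, and make that choice after seeing the data.

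**Working it through.** **1. The passages side by side**

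| Section | Who is compared | Condition |
|---|---|---|
| 1.1, 3, 9.1 | ADAPT vs waitlist | none stated |
| 9.3 | one modified intent-to-treat set | has a post-randomization assessment |
| 9.6, Aim 1 | ADAPT completers vs waitlist | completion, ADAPT arm only, undefined |
| 9.6, Aim 2 (prediction) | those completing ADAPT vs waitlist | same |

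A child who does not finish ADAPT but attends the post assessment is in the 9.3 set and outside the 9.6 comparison. Sections 8 and 10.1 plan to collect that child's data, so the two sets can differ under the plan's own rules.

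**2. The plan's own numbers (section 4)**

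- 124 × 0.75 = 93 agree.
- 93 × 0.65 = 60.45 qualify (plan: 60).
- 60 × 0.85 = 51 complete baseline (plan: 50).
- 50 × 0.90 = 45 retained.
- 45 × 0.90 = 40.5 usable (plan: 40).

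The figures reproduce to rounding. After baseline the only losses are study attrition and movement artifacts. There is no step for failing to complete ADAPT, so the funnel fits the 9.3 set better than a completer set. It gives about 22 retained, or 20 usable, per arm.

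**3. Size of the shift (assumptions, not document figures)**

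Let m of the n ADAPT children be returned non-completers whose change is s SD less favourable than that of the others. Assume no true treatment effect and the same latent share m/n in the waitlist, where nobody is removed. Dropping the m children raises the ADAPT mean by s × m/n, and the waitlist mean does not move. So bias = s × m/n towards ADAPT.

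| n | m | s = 0.5 | s = 1.0 |
|---|---|---|---|
| 22 | 1 | 0.023 | 0.045 |
| 22 | 2 | 0.045 | 0.091 |
| 20 | 1 | 0.025 | 0.050 |
| 20 | 2 | 0.050 | 0.100 |

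If such children would have changed more favourably, the sign reverses. If s = 0, the bias is 0.

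**4. Error rate for one two-group test**

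Simulation used a pooled t-test, unit SD and 60,000 runs per case. Nominal two-sided error is 5%.
- 22 vs 23 children, s = 0.5 and 1.0: 5.2% and 5.2% with m = 1; 5.3% and 5.9% with m = 2.
- 20 vs 20 children: 5.1% and 5.2% with m = 1; 5.4% and 5.8% with m = 2.
- Comparing the same simulated children as assigned: mean bias within 0.003 SD of zero.

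Hand check of the 22 vs 23 case with m = 2 and s = 1.0: after removal, 20 vs 23, SE = √(1/20 + 1/23) = 0.306, and 0.091/0.306 = 0.297. The normal tails are P(Z > 1.96 − 0.297) = 0.048 and P(Z < −1.96 − 0.297) = 0.012, which total 0.060. This agrees with the simulated 5.9%. The tail favouring ADAPT is 4.7% in the simulation, against a nominal 2.5%.

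**The case against.** The strongest reply is that 'completers' is loose wording for the 9.3 set. Sections 3 and 6.2.5 time the post assessment from the end of the assigned condition. Section 4 speaks of completed participants across both arms, and its funnel has no ADAPT non-completion step. Section 9.6 itself plans likelihood-based and not-at-random handling of missing data, which sits poorly with a deliberate completers-only analysis. Section 5.4 says the sample is too small to allow for adherence differences, and section 8 expects few discontinuers to return. The set that would be dropped is therefore small and may be empty.

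Most of this stands. It makes loose drafting plausible and the expected effect small. It does not remove the conflict, because no section equates a completer with someone who reached the post scan, and none ties 9.6 to 9.3. Section 8's low expectation concerns children who discontinue. It does not clearly cover a child who misses sessions but stays in contact and in the study.

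A reader might infer something stronger: that the sponsor has chosen a completers-only primary analysis, or that the result will be biased in favour of ADAPT. The documents support neither. The intent is unclear, no count of returned non-completers is given, and the direction of any difference is not stated. It would be equally wrong to infer that stopping has nothing to do with outcome, given the symptom-based route in section 8.

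**Conclusion.** The inconsistency is real and affects the primary comparison. Followed literally, 9.6 removes children from one arm on the basis of post-randomization behaviour under an undefined rule, and the contrast is then no longer by assigned arm.

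The likely size is small: about 0.02 to 0.10 SD and about 5 to 6% two-sided error. That rests on assuming 1 or 2 returned non-completers among 20 to 22 ADAPT children and a 0.5 to 1.0 SD less favourable change. Neither assumption comes from the documents. With no link the bias is zero, and with the opposite link it works against ADAPT. The error rates are for a single two-group test and do not carry over directly to whole-brain clusters at Z > 3.1.

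Severity is minor to should-fix. The numbers alone would make it minor. What raises it is that the primary analysis set should be settled before data are seen, and settling it costs almost nothing.

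**What to change.** - In 9.6, replace both completer phrases (Aim 1 and Aim 2) with *participants assigned to ADAPT*.
- In 9.3 and 9.6, state that the primary Aim 1 and Aim 2 comparisons use the modified intent-to-treat set by assigned arm. Include every randomized participant with usable post-assessment scan data, whatever number of ADAPT sessions they completed.
- Report attrition and unusable scans by arm.
- If a completer comparison is kept, define 'completer' in advance from the adherence data listed in 5.4 and label the comparison supportive.

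Section 8 and the FSL analysis stay as they are. The cost is a few sentences and one table by arm, with no new visits. The estimated effect may be slightly smaller than in completers, and because few discontinuers are expected back, the set may gain only a few children.

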#### 4. SELECTION AND ENROLLMENT OF PARTICIPANTS

The study population is male and female youth between the ages of 11-16 diagnosed with functional abdominal pain disorders (FAPD) and clinically significant anxiety. We plan to approach approximately 124 participants, ages 11-16 years. Of those, we expect 75% will agree to participate (n=93) based on our pilot fMRI study. Of those, we expect approximately 65% will qualify. Thus, we anticipate recruiting n=60 to complete a baseline assessment. Based on our previously RCT, we expect 85% of those recruited in clinic will complete the baseline assessment (n = 50) and the majority will be retained in the study (90%, n=45). Based on our fMRI pilot study, we expect to lose approximately 10% of participant data to movement artifacts yielding n=40 with usable data. The minimum number of total completed participants allowed will be 34 and the maximum will be 50.

We will recruit males and females to participate in this study. While FAPD is more common in females, we have found that we are easily able to recruit males as well. Based on our prior research projects, we expect that we will recruit a sample of youth with FAPD that is 65% female and 35% male. The PI ([name]) will check in with the mentorship team ([name] and [name]) quarterly regarding enrollment and gender breakdown in a blinded fashion. If the gender breakdown is skewed (>85% females or >60% males), the PI ([name]) will problem solve with study mentors ([name] and [name]) to ensure the sample is representative of the

population. Recruitment efforts would target candidates from underrepresented gender until the sample is more representative of the FAPD population.

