### 6.2.5 Completion/Final Evaluation

A post assessment (including fMRI) will be completed for all participants approximately one week after completion of treatment or waitlist. Participants will complete the same assessment measures and procedures as administered at the baseline assessment in addition to measures that were administered at screening. Upon completion of this visit, participants will receive a \$100 gift card (Amazon; described in further detail in 6.2.2. *Enrollment, Baseline, and Randomization*).

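### The modified ITT definition in Section 9.3 removes the expected dropouts before the missing-data methods of Section 9.6 can act, and the mixture MNAR models are unspecified and not identified from two scans

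*Combined protocol and SAP*

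**What the plan says.** Section 9.6 plans two missing-data methods. The general one is that "missing data will be handled via ML estimation with auxiliary correlate inclusion". For informative loss, "Missing not at random will be addressed with mixture MNAR methods"; example references follow, but no model, number of classes or patterns, identifying restriction or range of assumptions.

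The imaging analysis is described separately: "Analyses of both BOLD and ASL data will be accomplished via mixed effects ANOVAs", run in FSL from a seed to the whole brain. The section does not say how ML with auxiliary variables would be joined to that analysis. For Aim 1, the connectivity analysis is to "identify changes in functional connectivity between the AMY-PFC in ADAPT completers vs. those in the waitlist condition".

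Section 9.3 states that the analysis population "will be defined as those subjects who complete a post-randomization assessment".

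Section 6.2.5 describes the only imaging after randomization: "A post assessment (including fMRI) will be completed for all participants approximately one week after completion of treatment or waitlist". Section 4 expects 50 children to complete baseline, 45 to be retained and 40 to have usable imaging data, the last step being movement loss.

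Section 8 gives scheduling and distance as the common reasons for stopping ADAPT. It also says that ADAPT is discontinued when distress and pain increase, and that children who stop will probably not come back for assessment. Sections 8 and 10.1 commit to collecting endpoints after discontinuation where possible.

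**The concern.** The two sections work against each other. An MNAR method exists to deal with children whose outcome is missing for reasons tied to that outcome. Here those are mainly children with no post visit, and Section 9.3, read naturally, takes them out before any model is fitted. The Aim 1 wording goes further: it conditions the ADAPT arm on completing treatment and places no matching condition on the waitlist arm.

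Restoring these children would not make the named safeguard work as written. With a single post scan, nothing observed bears on the post value of a child who has left, so the answer depends on the constraint chosen, and the plan chooses none in advance.

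At stake is whether the ADAPT versus waitlist contrast remains a comparison of the groups as randomized. The waitlist has no treatment to stop during the comparison period, so loss tied to worsening symptoms would fall on the ADAPT arm and would tend to flatter it.

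**Working it through.** **1. The plan's own figures (Section 4).** Applying the stated percentages in turn:

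- 124 × 0.75 = 93 (stated 93)
- 93 × 0.65 = 60.45 (stated 60)
- 60 × 0.85 = 51 (stated 50)
- 50 × 0.90 = 45 (stated 45)
- 45 × 0.90 = 40.5 (stated 40)

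The cascade reproduces to within rounding.

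**2. Who is missing, and who stays in the set.**

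- No usable imaging data: 50 − 40 = 10 of 50, or 20%.
- Not retained: 50 − 45 = 5 of 50, or 10%. Section 9.3, read naturally, excludes them.
- Retained but lost to movement: 45 − 40 = 5 of 45, or 11%. They stay in the set, and ML could use their remaining scan and questionnaires.

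So about half of the expected missing outcomes are removed by definition and about half remain open to ML.

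**3. Size of the dropout group.** Assume 25 per arm at randomization (50/2). At 10% loss the expected number is 25 × 0.10 = 2.5 per arm. Under a binomial(25, 0.10), the probability of two or fewer dropouts in an arm is 54%, and of none 7%.

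**4. What two scans can identify.** Let y0 and y1 be the baseline and post values and R indicate whether y1 is observed. In pattern-mixture form:

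- a child with both scans contributes f(y0, y1 | R = 1) × P(R = 1);
- a dropout contributes f(y0 | R = 0) × P(R = 0).

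The mean of y1 given R = 0 appears in neither term, so the likelihood is flat in it. A numerical check on 50 simulated children with 5 dropouts gave a log-likelihood of −129.388 with that mean set at −2, −1, 0, 1 or 2 SD.

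Growth-type models meet the same limit. Two waves supply 2 means + 3 variances and covariances = 5 moments per group. A linear model with random intercept and slope needs 2 means + 3 variances and covariances + 1 residual variance = 6 parameters, before any latent class is added.

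**5. Possible size of the bias.** Let p be the fraction of the ADAPT arm that is missing and d the difference, in SD, between missing and observed ADAPT children. The arm mean shifts by p × d. The range d = 0.5 to 1.0 is assumed, with no such difference in the waitlist arm.

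- Loss spread evenly, p = 0.10: 0.10 × 0.5 = 0.05 and 0.10 × 1.0 = 0.10 SD.
- All five dropouts in ADAPT, p = 5/25 = 0.20: 0.20 × 0.5 = 0.10 and 0.20 × 1.0 = 0.20 SD.

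Against the effect of 0.4 in Section 9.2, taken as a standardized difference, even loss gives 0.05/0.4 = 12.5% to 0.10/0.4 = 25%. The extreme case gives up to 0.20/0.4 = 50%.

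**6. Against sampling error.** With 20 usable children per arm, the standard error of an unadjusted difference is √(2/20) = 0.32 SD. A shift of 0.05 to 0.10 SD is about one-sixth to one-third of that.

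**The case against.** A reader might infer that missing outcomes are not handled at all. The documents do not support this. ML with auxiliary variables is planned, and about 5 of the 10 expected missing outcomes belong to children who remain in the set. What is missing for them is a statement of how ML connects to a whole-brain FSL analysis.

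The boundary in Section 9.3 is also looser than a post scan. It asks only for an assessment after randomization, and Section 10.1 lets families complete post measures at home. A child with questionnaires but no scan could therefore stay in. Excluding full dropouts is the natural reading, not the only one.

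A reader might infer from Section 8 that loss is probably related to response. That section names logistic causes as the common ones and commits to seeking endpoint data. It supports informative loss in the ADAPT arm as a possibility, no more. Nor should the 0.10 to 0.20 SD range be read as the effect of the whole 20% without usable data, because the argument about children who stop ADAPT does not extend to movement artifacts.

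The plan's MNAR wording is open-ended, and a pattern-mixture model with a fixed offset would fit within it. Such a model rests on an assumption just as a tipping-point analysis does. This stands: the provable defect is that no model or constraint is specified, not that every mixture method is unusable. The advantage of a tipping-point analysis is that its assumption is visible.

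**Conclusion.** The point holds for children lost to follow-up. As naturally read, Section 9.3 removes the expected 5 of 50 before the methods in Section 9.6 apply, and the completer wording for Aim 1 points the same way. For those children a mixture MNAR result cannot be learned from one baseline and one post scan, and the plan gives no constraint to supply it.

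The likely size is modest: a shift of 0.05 to 0.10 SD in the ADAPT mean, rising to 0.20 SD only in the extreme split. It rests on three assumptions that the documents do not supply: a 0.5 to 1.0 SD difference, its confinement to ADAPT, and 25 children per arm. This should be corrected before analysis. It does not show that the trial's result would be wrong.

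**What to change.** - **Section 9.3:** define the primary population as all randomized children, analysed in the arm assigned.
- **Section 9.6, Aim 1:** replace the reference to ADAPT completers with all children randomized to ADAPT.
- **Primary imaging analysis:** keep the planned seed-to-whole-brain analysis. Replacing it with a single extracted value would be a separate and debatable change.
- **Missing-data analysis:** apply the planned ML, with baseline and named auxiliary variables, to one amygdala–prefrontal connectivity value extracted from a pre-specified region.
- **MNAR sentence:** replace it with a pre-specified delta-adjusted (tipping-point) analysis. For example, shift the missing ADAPT post values by 0 to 1 SD in the unfavourable direction and report where, if anywhere, the conclusion changes.

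The cost is SAP wording, one extracted measure and a short additional analysis, with no new data. The delta range remains an assumption, but it would be fixed in advance and open to the reader's judgement.
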